#### **8.6.2. Clinical Laboratory Parameters**

All clinical laboratory parameters will be listed; any value outside the clinical reference range will be flagged. Separate listings will be provided for any parameter for which there is any individual subject value outside the respective clinical reference range.

Summary tables and boxplots by treatment and timepoint will be provided for clinical chemistry, haematology, and coagulation.

Values recorded as  $< x$ ,  $\leq x$ ,  $> x$ , or  $\geq x$  will be displayed in the listings as recorded. For the derivation of listing flags, all calculations, and presentation in the figures,  $< x$  and  $\leq x$  values will be set to half of  $x$ , whereas  $> x$  and  $\geq x$  values will be set to  $x$ .

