8.4. Safety Analysis

Safety parameters will be listed and summarised using descriptive statistics. No formal statistical analysis of safety data is planned. Each AE will be coded using the Medical Dictionary for Regulatory Activities (MedDRA).

If conducted, the results from the cardiodynamic ECG assessment will be reported separately. Further detail of the analyses will be covered by the standard operating procedures (SOPs) and/or the analysis plan of the cardiac vendor.

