## 1. INTRODUCTION

This SAP has been developed after review of the clinical study protocol (Final Version 4 dated 06 October 2021) and electronic case report form (eCRF). Noting that later clinical study protocol (Final Version 5 dated 11 July 2022) was generated but never used for the study conduct.

This SAP describes the planned analysis of the pharmacokinetic (PK) safety, and tolerability data from this study. A detailed description of the planned TFLs to be presented in the clinical study report (CSR) is provided in the accompanying TFL shells document.

Continuous 12-lead electrocardiogram (ECG) data will be collected and stored for the future assessment of the NST-6179 concentration QT interval corrected for heart rate (QTc) response relationship following single oral doses of NST-6179. This data is not planned to be analysed by Labcorp Drug Development. If it decided to perform analysis on this data, this will be reported separately.

In general, the analyses are based on information from the protocol, unless they have been modified by agreement with NorthSea Therapeutics B.V. A limited amount of information about this study (eg, objectives, study design) is given to help the reader's interpretation.

This SAP must be finalised prior to any unblinding of study data for analysis purposes (interim or final). Additionally, the SAP and TFL shells should be finalised prior to any programming activities commencing.

This SAP supersedes any statistical considerations identified in the protocol; where considerations are substantially different, they will be so identified. If additional analyses are required to supplement the planned analyses described in this SAP, they may be performed and will be identified accordingly in the CSR. Any substantial deviations from this SAP will be agreed with NorthSea Therapeutics B.V and identified in the CSR.

This SAP is written with consideration of the recommendations outlined in the International Conference on Harmonisation (ICH) E3 guideline *Structure and Content of Clinical Study Reports*, ICH E8 guideline *General Considerations for Clinical Trials*, and ICH E9 guideline *Statistical Principles for Clinical Trials*.

The document history is presented in [Appendix 1](#).

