## **3. STUDY ENDPOINTS**

### **3.1. Primary Endpoints**

The primary safety endpoints for this study are as follows:

- incidence and severity of adverse events (AEs)
- incidence of laboratory abnormalities, based on haematology, clinical chemistry, coagulation, and urinalysis test results
- 12-lead ECG parameters
- vital signs measurements
- physical examinations.

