#### **8.6.5. Other Assessments**

Medical history will not be listed.

The continuous 12-lead ECG data will be recorded for this study, but if it is analysed in the future, it will be reported separately.

All other safety and tolerability assessments not detailed in the above sections will be listed only.

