### **10. SIGNIFICANT CHANGES FROM THE PROTOCOL-SPECIFIED ANALYSES**

There were no significant changes from the protocol-specified analyses.

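### The SAP text gives no by-treatment subject count for the primary endpoint on laboratory abnormalities, and no summary at all for urinalysis

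*SAP*

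**What the plan says.** Protocol 2.2.1 and SAP 3.1 list the primary safety endpoints in matching terms. One is the "incidence of laboratory abnormalities, based on haematology, clinical chemistry, coagulation, and urinalysis test results". It is a separate bullet from the incidence and severity of adverse events (AEs).

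The laboratory analysis is in SAP 8.6.2. All parameters are listed, and "any value outside the clinical reference range will be flagged". Any parameter with at least one out-of-range value also gets its own listing. The summaries are these: "Summary tables and boxplots by treatment and timepoint will be provided for clinical chemistry, haematology, and coagulation". Urinalysis is not among them. SAP 8.6.5 adds a default: "All other safety and tolerability assessments not detailed in the above sections will be listed only".

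Protocol 8.4 states: "Safety parameters will be listed and summarised using descriptive statistics". SAP 1 states: "This SAP supersedes any statistical considerations identified in the protocol; where considerations are substantially different, they will be so identified". SAP 10 then records: "There were no significant changes from the protocol-specified analyses".

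SAP 1 also points to a companion document: "A detailed description of the planned TFLs to be presented in the clinical study report (CSR) is provided in the accompanying TFL shells document". That document was not supplied.

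**The concern.** The endpoint is defined as an incidence, so it needs three things: a rule for what counts as abnormal, a set of values to which the rule applies, and a count of subjects by treatment. The laboratory section of the SAP specifies none of them as such. Its summaries describe the distribution of values at each visit, which answers a different question.

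At stake is whether a named primary endpoint of a first-in-human safety study is reported by a rule fixed in advance. If it has to be assembled later from listings, whoever does so must decide what an abnormality is and which draws count, with the data in view.

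The panel without any summary is also not an idle one. Protocol 1.4.3 reports tubular nephropathy in one high-dose monkey, with its relation to the death still under investigation. The protocol says exposures there were far above those likely in this study, and serum creatinine is among the summarised tests. Even so, urinary protein and blood would appear in listings only.

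**Working it through.** The documents state no figure on this point, so the check is a comparison of text plus a count of what is affected.

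**1. Planned output by panel (SAP 8.6.2)**

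| Panel | Flagged listing | Separate listing if any value is out of range | Value summary by treatment and timepoint | Subjects with an abnormal value, by treatment |
|---|---|---|---|---|
| Clinical chemistry | yes | yes | yes | none specified |
| Haematology | yes | yes | yes | none specified |
| Coagulation | yes | yes | yes | none specified |
| Urinalysis | yes | yes | no | none specified |

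Panels with any by-treatment summary: 3 of 4. Panels with a by-treatment subject count: 0 of 4.

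**2. Can the value summaries stand in for the incidence?** No. SAP 8.1.2 implies that the tables show a minimum and a maximum. A maximum above the upper limit shows that at least one subject was out of range at that visit. It does not show how many were, or whether the same subject was out of range at the next visit. The number of distinct subjects cannot be recovered from visit-level summaries.

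**3. Can the AE tables stand in?** Only in part. SAP 8.6.1 gives subject frequencies by preferred term and treatment. Under protocol Appendix 1, a laboratory finding falls within the AE definition when it is clinically significant, so the tables cover that subset.

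**4. Which values would be counted?** Under SAP 8.1.4, any additional laboratory value is unscheduled and is left out of all calculations except the baseline derivation. Under SAP 8.1.2, discontinuation values are in general left out too, with exceptions allowed. SAP 8.1 says listings cover all captured data except medical history. A hand count from listings would therefore include unscheduled values, while a count following 8.1.4 would not. The SAP does not say which applies to the incidence.

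**5. Share of tests without a summary.** From protocol Appendix 2, leaving out the lipid panel that applies only from Cohort B4:
- Chemistry 18 + haematology 13 + coagulation 3 = 34 tests with value summaries.
- Urinalysis 8 tests without. Total 34 + 8 = 42, and 8/42 = 19.0%.

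**6. Scheduled postdose urinalysis visits without a summary.** Subjects dosed are from protocol Table 8 and section 1.6.1.2; visits are from Appendix 6.
- Part A, A1 to A5: 5 × 8 = 40 subjects, with 2 postdose visits (48 h and follow-up): 40 × 2 = 80.
- Part B, B1 to B3: 3 × 10 = 30 subjects, with 4 postdose visits (Day 4, Day 8, 48 h after the Day 14 dose, follow-up): 30 × 4 = 120.
- Total 40 + 30 = 70 subjects, matching the 70 stated, and 80 + 120 = 200 subject-visits if all attend.

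**7. Protocol version.** The SAP was written from protocol Version 4; the protocol supplied is Version 5. The Version 4 to 5 change log reports no change to section 8.4 or to the primary endpoints, so the comparison stands.

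**The case against.** The strongest reply is that nothing is missing except a tabulation. The separate out-of-range listings cover any parameter, urinalysis included. With 6 active subjects in a Part A group and 8 in a Part B group, n/N can be counted by hand. This stands, and it limits the point: the endpoint is recoverable. What it does not supply is a definition or a rule on which draws count.

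A second reply is that an abnormality could mean a clinically significant one. Protocol 1.6.1.2 describes interim laboratory results in those terms, and on that reading the AE tables already give a count by treatment. This is possible, because neither document defines the term. But the endpoint is listed apart from AEs and is tied to test results in four panels, and the SAP's only operational marker is the reference-range flag. The ambiguity is itself a reason to define the term.

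Third, the TFL shells may contain exactly this table. That cannot be checked, so the point concerns the SAP text only.

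A reader might infer that SAP 10 is simply wrong. The documents do not go that far. Protocol 8.4 promises descriptive summaries, not an abnormality count, and three of four panels are summarised. Only urinalysis departs from it. Whether that is a significant change, or a substantially different consideration under SAP 1, is a judgement.

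A reader might also extend the point to vital signs. That endpoint is the measurements themselves, not an incidence, and SAP 8.6.3 summarises both values and changes from baseline. No corresponding gap is shown there.

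**Conclusion.** The concern holds for the SAP text. A primary endpoint defined as an incidence over four panels has no by-treatment subject count for any of them. Urinalysis, 8 of 42 tests and 200 scheduled postdose subject-visits in the 70 subjects dosed, has no summary, which departs from protocol 8.4. The visit figure assumes full attendance.

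A reader might conclude that the endpoint has been dropped or the data lost. The documents do not support this: the values are listed, flagged and partly summarised, and the unseen shells may close the gap. Nor can the documents show how far a hand count would differ under different definitions, since they give no abnormality rates.

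The consequence is limited to reporting. No inferential safety analysis is planned (SAP 8.6.6), so no error rate or sample size changes. Dose escalation relies on interim safety reports and the criteria in protocol 3.6 and 3.7, not on these tables. The gap still merits correction, because it concerns a named primary endpoint and the remedy is cheap.

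**What to change.** In SAP 8.6.2:

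- Define a laboratory abnormality, for example by the SAP's own out-of-range flag.
- Add a descriptive table by treatment, pooled placebo included, of n/N subjects with at least one postdose abnormal value. Give it per parameter for all four panels, with direction (low or high) where applicable. For urinalysis this also supplies the summary that protocol 8.4 calls for.
- Make scheduled visits the main count and show alongside it the count that includes unscheduled and discontinuation values. Subjects sampled more often have more chances to be counted, so the two should be kept apart.
- If the TFL shells already contain this table, name it in the SAP text.

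The by-timepoint summaries can stay. The wording should be settled before unblinding, the point by which SAP 1 requires the plan to be final.

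The cost is SAP wording and a few extra tables from data already collected. The downside is that some isolated or artefactual out-of-range values will be counted. In groups this small the counts are descriptive only and should be labelled so.

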Appendix 2: Clinical Laboratory Evaluations

Clinical chemistry:	Haematology:	Urinalysis:
Alanine aminotransferase (ALT)	Haematocrit	Blood
Albumin	Haemoglobin	Glucose
Alkaline phosphatase (ALP)	Mean cell haemoglobin	Ketones
Aspartate aminotransferase (AST)	Mean cell haemoglobin concentration	pH
Calcium	Mean cell volume	Protein
Chloride	Platelet count	Specific gravity
Cholesterol	Red blood cell (RBC) count	Urobilinogen
Creatinine	White blood cell (WBC) count	Microscopic examination
Direct bilirubin	WBC differential:	
Gamma-glutamyl transferase (GGT)	Basophils	Coagulation profile:
Glucose	Eosinophils	Activated partial thromboplastin time (aPTT)
Inorganic phosphate	Lymphocytes	International normalized ratio (INR)
Potassium	Monocytes	Prothrombin time (PT)
Sodium	Neutrophils	
Total bilirubin		
Total CO ₂		
Total protein		
Uric acid		
Serology:^a	Drug screen:	Hormone panel - females only:
Anti-hepatitis B surface antibody	Including but not limited to:	Follicle-stimulating hormone (FSH) ^a
Hepatitis B surface antigen (HBsAg)	Amphetamines/methamphetamines	Serum pregnancy test (human chorionic gonadotropin) ^b
Hepatitis C antibody	Barbiturates	Urine pregnancy test ^b
Human immunodeficiency virus (HIV-1 and HIV-2) antibodies and p24 antigen	Benzodiazepines	
	Cocaine (metabolite)	
	Methadone	
	Phencyclidine	
	Opiates	
	Tetrahydrocannabinol/cannabinoids	Fasting Lipid Panel (Cohorts B4 onwards):
	Tricyclic antidepressants	Low-density lipoprotein cholesterol (LDL-c)
	Cotinine test	High-density lipoprotein cholesterol (HDL-c)
		Very low-density lipoprotein (VLDL)
		Total Cholesterol
		Triglycerides (TG)
		Apolipoprotein (Apo) A1
		ApoB
		ApoC3

a. Performed at screening only.

b. For all female subjects, performed in serum at screening and in urine at all other times. A positive urine pregnancy test will be confirmed with a serum pregnancy test.

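### One substitution rule for all censored laboratory values (SAP 8.6.2) can misplace out-of-range flags for parameters whose normal range lies far from zero

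*SAP*

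**What the plan says.** SAP 8.6.2 governs laboratory results recorded with an inequality sign.

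- **Display.** Such results "will be displayed in the listings as recorded", so a listing prints the inequality itself.
- **Substitution.** "For the derivation of listing flags, all calculations, and presentation in the figures", results of the form `<x` and `≤x` are treated differently: these "values will be set to half of" x. Results of the form `>x` and `≥x` are set to x. No parameter is excluded. SAP 8.1 defines the term for all calculations broadly; it covers summary statistics and baseline derivation among others.
- **Flags.** "any value outside the clinical reference range will be flagged". In addition, "Separate listings will be provided for any parameter for which there is any individual subject value outside the respective clinical reference range".
- **Summaries.** "Summary tables and boxplots by treatment and timepoint will be provided for clinical chemistry, haematology, and coagulation". Urinalysis is not in that list.

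The panel in Protocol Appendix 2 contains urine pH and "Specific gravity", and the clotting tests aPTT, INR and PT. SAP 3.1 names as a primary safety endpoint the "incidence of laboratory abnormalities, based on haematology, clinical chemistry, coagulation, and urinalysis test results".

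Neither document gives reporting limits or reference ranges, or says which parameters the laboratory ever reports as censored.

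**The concern.** Replacing a value below a bound by half that bound is a reasonable convention when zero is the natural floor and the bound is close to it, as for a low bilirubin. It is not reasonable when the whole plausible range sits well away from zero. A specific gravity bound near 1 becomes about 0.5, whereas SAP 8.5.1.3 itself takes 1 g/mL as the working value for urine. A pH bound is halved on a scale where halving has no meaning.

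The SAP uses the substituted number, not the recorded inequality, to decide whether a result is out of range. A result compatible with normality can therefore acquire a low flag and put its parameter into the separate abnormal listings. The listing would show the recorded inequality next to the flag, without the number that produced it. The upper rule can err the other way, leaving a result that is certainly high unflagged.

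Section 8.6.2 plans no table that counts abnormalities. The flags and the listings they trigger are thus the outputs that identify individual abnormal results for this endpoint. For urinalysis they are the only planned output.

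**Working it through.** **Inputs.** The substitution and flag rules are from SAP 8.6.2 and the panel from Protocol Appendix 2. Active group sizes are 6 in Part A and 8 in Part B (Protocol 3.1.1 and 3.1.2). All bounds x and reference limits below are assumptions, since the documents give none. The plan states no figure to reproduce.

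**Step 1: when a low flag can be wrong.** Let L be the lower reference limit. The rule flags low when x/2 < L, that is, x < 2L. The true value may still be in range when x > L (for `<x`) or x ≥ L (for `≤x`). A low flag can therefore be wrong when:

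- `<x`: L < x < 2L
- `≤x`: L ≤ x < 2L

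If L = 0 this window is empty, so such analytes have no flag problem. For specific gravity with L near 1, the window runs to about 2 and covers every realistic bound at or above L.

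**Step 2: numbers put in.**

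| Recorded | Assumed L | x/2 | Flag under SAP | What is known |
|---|---|---|---|---|
| Specific gravity `≤1.005` | 1.001 or 1.005 | 0.5025 | low | may be normal |
| Specific gravity `<1.005` | 1.005 | 0.5025 | low | certainly low |
| pH `≤5.0` | 4.5 or 5.0 | 2.5 | low | may be normal |
| pH `<5.0` | 5.0 | 2.5 | low | certainly low |
| INR `<0.9` | 0.8 | 0.45 | low | may be normal |
| INR `<0.8` | 0.8 | 0.40 | low | certainly low |
| aPTT `<24` s | 22 s | 12 s | low | may be normal |
| aPTT `<20` s | 22 s | 10 s | low | certainly low |
| PT `<10` s | 9.5 s | 5.0 s | low | may be normal |
| PT `<9` s | 9.5 s | 4.5 s | low | certainly low |
| GGT `<10` | 6 | 5 | low | may be normal |
| Total bilirubin `<3` | 0 | 1.5 | none | not low |

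The outcome turns on where x lies relative to L. The GGT row shows that an analyte with a natural floor of zero can also be affected if its lower reference limit is above zero.

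**Step 3: the upper side.** Let U be the upper limit. Setting the value to x gives a high flag only when x > U. If x = U, a result `>x` is certainly above U but is not flagged (for example pH `>8.0` with U assumed 8.0). A result `≥x` with x = U may equal U and be in range, so leaving it unflagged as high is not an error. With x above U (pH `>9`, U = 8.0) the flag is correct.

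**Step 4: summary tables (coagulation).** Replacing one value x by x/2 lowers a mean of n values by x/(2n). Take one aPTT recorded as `<20` s, with the other subjects at 28 s:

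- n = 6: (5 × 28 + 10)/6 = 25.0 s with x/2; (5 × 28 + 20)/6 = 26.67 s with x; difference 1.67 s.
- n = 8: (7 × 28 + 10)/8 = 25.75 s with x/2; (7 × 28 + 20)/8 = 27.0 s with x; difference 1.25 s.

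**Step 5: using x for flags is not enough.** Specific gravity `<1.005` with L = 1.005 is certainly low, yet 1.005 is not below 1.005, so it would go unflagged. Flags need the inequality, not a substituted number.

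**The case against.** The strongest reply is that the harm may never arise. Nothing in the documents shows that pH, specific gravity or the clotting tests are reported as censored, and where they are not, the rule does nothing. Even where they are, the low flag is right whenever the recorded interval lies wholly below the lower limit, as five rows of the table show. All of this stands, and it makes the problem conditional.

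Further points also stand. Halved clotting times and INR are implausible, not strictly impossible. The halved pH and specific gravity are never printed, and 8.6.2 plans no urinalysis summaries or boxplots. The missed high flag needs x to coincide exactly with the upper limit. Protocol 7.2.2 has an investigator or designee assess all laboratory data clinically, and Protocol Appendix 1 lets a clinically significant abnormal result count as an adverse event, so clinical judgement does not depend on the SAP flag. The liver-test criterion in Protocol 3.7 concerns increases confirmed on repeat, which false low flags do not touch.

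What the reply does not do is justify the rule. A prespecified derivation should be valid for every parameter it covers, and this one covers parameters for which half the bound carries no information about normality.

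**Conclusion.** The concern holds as a conditional, minor point. SAP 8.6.2 applies one substitution to all laboratory parameters and derives flags from it. For parameters whose plausible range is far from zero, this can flag possibly normal results low, and it misses a certain high when `>x` has x equal to the upper limit.

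The effect is limited to flags and separate abnormal listings, plus summary tables and boxplots for coagulation. In the illustration, one censored aPTT makes a group mean 1.25 to 1.67 s lower than using the bound itself. These sizes rest on assumed bounds and limits.

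A reader might infer that normal results will be falsely flagged, or that the primary safety endpoint is compromised. The documents do not support either reading: they give no reporting limits or reference ranges, do not show that these parameters are ever censored, and plan no inferential safety analysis (SAP 8.6.6).

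**What to change.** Amend SAP 8.6.2 in two places.

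1. **Flags.** Derive them from the recorded inequality by comparing the whole censored interval with the reference range, for every parameter:
   - `<x` is low if x is at or below the lower limit.
   - `≤x` is low only if x is below the lower limit.
   - `>x` is high if x is at or above the upper limit.
   - `≥x` is high only if x is above the upper limit.
   - A censored result whose interval straddles a limit is marked indeterminate.
2. **Summaries and figures.** Restrict x/2 to analytes whose natural floor is zero. Use x for pH, specific gravity, INR, PT and aPTT, naming these parameters in the SAP.

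The cost is SAP wording, a short parameter list and one extra flag category in the derivation program. No new data are needed. Checking with the laboratory which parameters it reports as censored would show whether the change affects any result in this study.
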